Randomization

After randomization, patients will have a brief post-enrollment nutrition/exertion/satiety counseling and assessment.

Procedure

This includes a patient visit for procedure which may or may not include an admission for a 23-hour observation for symptom management, further elaborated in section 5.5.

Anthropomorphic and vital signs data will also be collected on procedure day.

Post-Op Call

This is a telephone visit which will include review of adverse events and medications.

Week 1

This will include:

- Focused physical examination
- Anthropomorphic and vital signs data
- Review of adverse events and medications
- Nutritional counseling and assessment.

Week 4(Month 1)

This will include:

- Anthropomorphic and vital signs data
- Review of adverse events and medications
- Nutritional counseling and assessment.

Week 8(Month 2)

This will include:

- Anthropomorphic and vital signs data
- Review of adverse events and medications
- Nutritional counseling and assessment.

Week 12 (Month 3)

This will include:

-
- Questionnaires
- Anthropomorphic and vital signs data
- Review of adverse events and medications
- Nutritional counseling and assessment.

Weeks 16, 20

These will include:

- Anthropomorphic and vital signs data
- Review of adverse events and medications
- Nutritional counseling and assessment.

Week 26 (Month 6)

This will be a comprehensive visit, including:

- Complete physical examination
- Anthropomorphic and vital signs data
- Review of adverse events and medications
- Laboratory testing
- Questionnaires
- EGD, to be performed clinically
- MRI
- Gastric emptying scintigraphy
- Nutritional counseling and assessment.
- Inter-observation of deidentified EGD video by qualified endoscopist

Weeks 30, 36, 42, 48

These will include:

- Anthropomorphic and vital signs data
- Review of adverse events and medications
- Nutritional counseling and assessment.

Week 52 (Year 1)

This will include:

- Complete physical examination
- Anthropomorphic and vital signs data
- Review of adverse events and medications
- Laboratory testing
- Questionnaires
- Nutritional counseling and assessment.

Unscheduled Visit

Any unscheduled visits will include a complete physical examination collection of anthropomorphic and vital signs data and review of adverse events and medications.

DATA MONITORING AND SAFETY REPORTING

Data and Safety Monitoring

This study will adhere to an IRB approved data safety monitoring plan (DSMP) to ensure sufficient oversight of the following areas of study conduct: subject safety, data integrity, subject privacy, data confidentiality, product accountability, study documentation and study coordination. Monthly meetings will be held with the Principal Investigator in attendance to review study conduct, with additional meetings to occur as needed to address time sensitive matters including adverse events or any deviations. Internal monitoring will be conducted following the accrual of the first subject, with additional monitoring to be undertaken on a quarterly basis thereafter. All adverse events, deviations and unanticipated problems affecting subject safety will be reported according to the requirements of the IRB of record. Ongoing assessment of AEs by the PI will determine if any of the stopping rules have been triggered.

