- Improvement in obesity related comorbidities (blood pressure, fasting glucose, HbA1c, lipid panel, liver enzymes) at 6 and 12 months compared to baseline.
- Changes in gastric motility, volume, accommodation, and constructed gastroplasty on MRI at 6 months compared to baseline.
- Changes in gastric emptying evaluated by gastric emptying study at 6 months compared to baseline.
- Changes in liver biochemical panel, and glucose homeostasis parameters at 6 months compared to baseline between the two groups.

Safety

- The incidence, frequency, and severity of adverse events related to treatment with the device will be reported throughout the duration of the study.
- Goal is <5% rate of serious adverse events related to the device or procedure (as determined by the site PI). Serious adverse events will be classified in the Adverse Events table.

Study Setting

The study will be conducted at 1 US center, Mayo Clinic in Rochester, MN. The maximum enrollment will be limited to 24 participants. The expected enrollment period is 6 months.

Subjects

Participants will be adult patients (Ages 21 \geq and \leq 65) with a BMI \geq 30 and \leq 40 kg/m² that meet the eligibility criteria below. All eligibility criteria must be met at the time of randomization.

Inclusion Criteria

1. Age 21-65
2. BMI \geq 30 and \leq 40 kg/m²
3. Willingness to comply with the substantial lifelong dietary restrictions required by the procedure.
4. History of failure with non-surgical weight-loss methods.
5. Willingness to follow protocol requirements, including signed informed consent, routine follow-up schedule, completing laboratory tests, and completing diet counseling.

6. Residing within a reasonable distance from the investigator's office and able to travel to the investigator to complete all routine follow-up visits.
7. Ability to give informed consent.
8. Women of childbearing potential (i.e., not post-menopausal or surgically sterilized) must agree to use adequate birth control methods.

Exclusion Criteria

1. History of foregut or gastrointestinal (GI) surgery (except uncomplicated cholecystectomy or appendectomy).
2. Prior gastrointestinal surgery with sequelae, i.e. obstruction, and/or adhesive peritonitis or known abdominal adhesions.
3. Prior open or laparoscopic bariatric surgery.
4. Prior surgery of any kind on the esophagus, stomach, or any type of hiatal hernia surgery.

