Figure 1. Study Flow Diagram

Screening and Eligibility assessment

Screening will be conducted by the investigator or the co-investigator and documented on the Investigator delegated/medically qualified team member intake form (conventionally known as PI Intake Form) and Screening Labs form. Screening must occur no more than 45 days prior to randomization.

Screening will include the following:

1. Sign informed consent form
2. Screening exam and intake by the investigator or co-investigator
3. Height, weight, and BMI; waist and hip circumference; vital signs (blood pressure and pulse)
4. Dietary screening intake and approval
5. Laboratory tests (after 8 hours fasting)
 - **CBC:** hemoglobin, hematocrit, white blood cell count, mean corpuscular volume, platelets
 - **Chemistry panel:** sodium, potassium, chloride, CO₂, BUN, creatinine, fasting glucose, fasting insulin, SGOT/AST, SGPT/ALT, alkaline phosphatase, total bilirubin, direct bilirubin, albumin, fasting lipids profile (total cholesterol, triglyceride, LDL cholesterol, HDL cholesterol), Ferritin, B12, C-reactive protein.
 - **Coag:** INR, PTT
 - **Urinalysis**
 - **HgbA1C**
 - **H. Pylori Breath Test.** **Patients with a positive h-pylori breath test will be treated and eradication must be confirmed with a stool antigen after treatment and prior to randomization**
 - **EKG** for all patients
 - **Urine pregnancy test** for women of child-bearing potential^a
 - **MRI** at baseline to evaluate gastric anatomy, gastric motility, and gastric accommodation.
 - **Gastric emptying scintigraphy** at baseline to evaluate gastric emptying. Gastric emptying scintigraphy will be conducted according to current Mayo Clinic Rochester clinical protocol.
6. Questionnaires
7. Psychological evaluation and approval: Study psychologists will use their standard clinical evaluations for bariatric interventions.

Within one week (7 calendar days) of completion of the screening tests, the PI will review the results and determine the participant's eligibility. The center will inform the participant of their screening results within 10 days of completing testing. Any abnormal lab results will be communicated to the participant by delegated personnel, and they will be required to notify their primary care provider (PCP) for any further action that may be necessary. All potential participants who qualify for randomization based on the initial

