^a Childbearing potential to be defined as women who are not yet post-menopausal who are not consistently utilizing an acceptable form of contraception. Acceptable forms of contraception to include hormonal methods such as oral contraceptives, patches, injections, vaginal ring, or implants, hormonal or copper intrauterine device, or history of surgical sterilization including tubal ligation or hysterectomy.

screening assessments will have the chance to review any questions with the study staff, as well as a recap of the follow-up schedule, and they will then receive their randomization assignment.

Recruitment efforts will be made by working with Mayo Clinic's Research Recruitment Services to develop marketing materials including a recruitment flyer in both print and digital formats, a social media recruitment plan leveraging Mayo Clinic's enterprise social media accounts for recruitment and other potential tactics to be determined after recruitment begins, directed towards the goal of boosting minority inclusion to be at least representative of the local population. Data will be pulled during the time of IRB submission and included to establish general targets justifying Exclusion #35 to help reserve spots for enrollment that are in-line with a representative population if they are not met by a certain threshold. At the time of this writing, Rochester, MN has demonstrated approximately 10% minority population.

Randomization

Participants will be randomly assigned to treatment or control group with a 1:1 allocation per a computer-generated randomization using variable block randomization.

Participants will be blinded to the results of randomization. They will remain blinded until the end of the study, or if there is medical or surgical safety concern. If any SAEs occur, subjects may be unblinded as defined by the Clavien-Dindo Grade III or above. Unblinding of subjects will be reported to IRB per local site IRB guidelines, if not meeting the criteria above. Measures will be taken to minimize or avoid bias in the study using "masking/blinding procedures." Randomization assignment will be recorded in the EDC and subject tracking, but will not be recorded within the EMR to reduce clinical team exposure to their randomized status for follow-up care. Research teams will not be blinded to the randomization results. Subjects will be asked to confirm with their study team if they have become aware of the procedure.

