Participants will proceed to a brief visit with the dietician to review the post-op liquid diet, and the procedure (ESG or HAPC/ESG) will be scheduled within 60 days of randomization.

Trial Intervention

Participants will report to the procedure suite within 60 days of randomization. Participants of child-bearing potential will be required to have a pregnancy test within 7 days of the scheduled ESG or combined HAPC and ESG. Participants taking medications for hypertension and/or type II diabetes will be instructed to notify their prescribing physician of their procedure and to discuss any necessary medication changes for the post-op period.

The ESG or combined HAPC and ESG will be conducted in Saint Marys Hospital at the Mayo Clinic in Rochester, Minnesota. Within two hours prior to the procedure, IV access will be obtained, IV hydration initiated, and a transdermal scopolamine patch placed for patients 65 years of age or younger (this will be removed in 24 to 48 hours after the procedure). Scopolamine can precipitate delirium in elderly patients, and hence we will avoid using them in patients older than 65 years of age. After Hybrid ESG or traditional ESG patient will be monitored for 24-48 hours to ensure patient is able to tolerate liquid diet and discharge timing is to be determined on individual basis per the site primary investigator.

Prior to ESG or combined HAPC and ESG, a standard upper endoscopy is performed to rule out any contraindications. All procedures will be done under general anesthesia with endotracheal intubation and utilizing CO₂ insufflation. During the procedure, IV hydration will be continued, and patients will be given the following: one dose of IV antibiotics (Zosyn, Ceftriaxone, or Ciprofloxacin), 8 mg of IV Zofran, and 8 mg of Decadron. A minimum of two liters of IV hydration (either normal saline or lactate ringers) should be administered in the perioperative recovery period before discharge. Sequential compression devices

(SCDs) will be used perioperatively to decrease the risk of deep vein thrombosis (DVT) and pulmonary embolism (PE).

Patients will be prescribed the following medications or equivalent after the procedure to manage expected post-procedural symptoms:

- Zofran 4mg rapid dissolving pills taken every 6 hours as needed for nausea for 7 days
- Phenergan 25mg suppositories taken twice daily as needed for nausea for 7 days
- Low dose liquid narcotic taken every 6 hours as needed for pain for 5 days

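### Two definitions of childbearing potential conflict: footnote a exempts users of hormonal or intrauterine contraception from the screening pregnancy test, and the pre-ESG test does not say which definition applies

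*Combined protocol and SAP*

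**What the plan says.** Inclusion Criteria, item 8, gives one definition: "Women of childbearing potential (i.e., not post-menopausal or surgically sterilized) must agree to use adequate birth control methods". Contraceptive use does not change a woman's status under it.

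Screening and Eligibility assessment lists a urine pregnancy test "for women of child-bearing potential", with a marker to footnote a. That footnote defines the term as "women who are not yet post-menopausal who are not consistently utilizing an acceptable form of contraception". Its accepted methods include "hormonal methods such as oral contraceptives, patches, injections, vaginal ring, or implants, hormonal or copper intrauterine device", as well as surgical sterilization.

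Exclusion 23 bars pregnant or breast-feeding patients, and the Subjects section says: "All eligibility criteria must be met at the time of randomization".

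Trial Intervention calls for a pregnancy test in the week before ESG or HAPC/ESG for participants of childbearing potential. It gives no definition and no footnote marker. The same section puts all procedures under general anesthesia.

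The Schedule of Events has two relevant notes. The double-asterisk note, on the pregnancy test row, restricts that test to females of childbearing potential without defining them. The triple-asterisk note, whose marker is on the gastric emptying scintigraphy row, asks for a point-of-care urine test 48 hours before an unnamed procedure, with an exception tied to a blood test. The Screening & Enrollment list repeats the childbearing-potential condition, again undefined.

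**The concern.** A pregnancy test requirement depends on knowing who must be tested. Here one term has two meanings, and the narrower one governs the screening test. A woman who satisfies inclusion 8 by using a listed method leaves the group that footnote a sends for testing. Her reported contraception then stands in for a test, yet contraception does not exclude pregnancy.

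Two things are at stake. The first is the evidence for exclusion 23 at randomization. The second is whether she is tested before an elective procedure under general anesthesia. Neither bears on the estimand, the sample size or any comparison between arms.

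**Working it through.** The protocol gives no figure to reproduce, so the check sets the definitions side by side and counts tests for one case: a premenopausal, unsterilized woman consistently using an oral contraceptive or an intrauterine device.

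**Step 1: status under each definition.**
- Inclusion 8: not post-menopausal and not sterilized, so she is of childbearing potential.
- Footnote a: consistently using a listed method, so she is not.

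The two agree on post-menopausal women, on sterilized women and on women using no accepted method. They disagree only on consistent users of the listed reversible methods.

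**Step 2: can one definition absorb the other?** If footnote a governed inclusion 8, a woman who complied through a listed method would drop out of the group the criterion addresses. The criterion would be circular. The definitions have to be reconciled by an edit.

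**Step 3: tests required by Screening and Eligibility assessment and by Trial Intervention.**

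| Reading | Screening | Pre-ESG | Total |
|---|---|---|---|
| Footnote a governs both | 0 | 0 | 0 + 0 = 0 |
| Footnote a governs screening only | 0 | 1 | 0 + 1 = 1 |
| Inclusion 8 governs both | 1 | 1 | 1 + 1 = 2 |

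The first two rows are both open on the current text: the marker fixes the screening entry at 0, and nothing fixes the pre-ESG entry. The third row is what inclusion 8 would imply.

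**Step 4: the triple-asterisk note.** It is kept out of the table because it states no population and does not say which procedure it means.
- Read by its row, it means scintigraphy. A urine test then precedes the Tc-99m meal, and the ESG question stays open.
- Read by the schedule's Procedure column, it means ESG. It then sits beside a 7-day requirement with a different window, and the scintigraphy is left to the screening test.
- Its exception refers to a blood test, but the screening list specifies urine and the schedule's laboratory list contains no blood pregnancy test.

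On its natural reading, by row, the note does not settle who is tested before ESG.

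**The case against.** The strongest reply is that the triple-asterisk note already supplies the missing test. Unlike the double-asterisk note, it carries no childbearing-potential restriction and no link to footnote a, and its marker is on the scintigraphy row. Scintigraphy is a screening item, so a test before the baseline study also comes before randomization and gives some support to exclusion 23. Much of this stands, and it limits the point.

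A reader might infer that a contraceptive user has no required test before the baseline Tc-99m meal. From the timing rules, "Screening must occur no more than 45 days prior to randomization" and "Participants will report to the procedure suite within 60 days of randomization", the same reader might add 45 + 60 = 105 days and conclude that her first test could come 105 − 7 = 98 to 105 days after the meal. The documents do not support this. Both statements hold only if the triple-asterisk note is disregarded or read as silently limited by footnote a, and its text states no such limit.

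Two other safeguards can be cited. One is the site's own practice: "Gastric emptying scintigraphy will be conducted according to current Mayo Clinic Rochester clinical protocol". That protocol is not in the documents, and whether it explains the blood-test exception cannot be determined. The other is exclusion 34, which gives the investigator discretion on safety grounds. Neither is a stated pregnancy test.

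The reply does not reach the conflict of definitions, the exemption from the screening test, or the unstated population for the pre-ESG test.

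**Conclusion.** The conflict is real and visible on the page. Followed as written, footnote a exempts consistent users of hormonal or intrauterine contraception from the screening urine test. If staff carry it over to Trial Intervention, such a woman could reach general anesthesia without a test required by either section.

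The size is 0 or 1 required tests across those two sections on the current text, against 2 under the inclusion 8 definition. The documents do not say how many of the 24 participants would be affected, and no count is claimed.

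The conclusion assumes that the footnote marker on the screening test means what it says, and that the triple-asterisk note applies to the row it marks. If that note were instead meant for ESG and for all women, the pre-ESG gap would largely close. The conflict of definitions and the screening exemption would remain.

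Severity is minor: a participant-safety and eligibility wording issue with no consequence for endpoints, power or analysis.

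**What to change.** 1. Replace footnote a with the inclusion 8 definition: childbearing potential means neither post-menopausal nor surgically sterilized.
2. Apply that definition to the screening test and to the test within 7 days of ESG or HAPC/ESG, and say explicitly that contraceptive use does not exempt anyone.
3. Move the list of accepted methods to inclusion 8, which asks for adequate birth control without defining it.
4. State that the triple-asterisk test precedes scintigraphy and covers the same women, and identify the blood test in its exception or delete the exception.

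The cost is protocol wording plus, per affected woman, 2 − 1 = 1 extra urine test if the pre-ESG test already reaches her, or 2 − 0 = 2 if it does not. On its natural reading the triple-asterisk test is already required, so clarifying it adds nothing. The extra tests fall within the existing screening and pre-procedure work-up of a 24-participant trial. Design, sample size, endpoints and analysis are unchanged.

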- Omeprazole 40mg capsule to be opened and mixed with smooth, semi-liquid food for the first 7 days after ESG or combined HAPC and ESG, then taken as whole capsule daily for 12 months from date of ESG or combined HAPC and ESG.
- Ativan 0.5 mg taken orally once daily for up to 3 days as needed for intractable nausea or anxiety.

Admission for a 23-hour observation for symptom management is optional but permissible. All patients will be given instructions prior to being discharged from the facility to help manage post-procedural symptoms, including nausea, vomiting and/or abdominal pain. Study staff will call patients once between 18-36 hours after the procedure to assess symptoms and to relay any issues to the PI. If the PI feels it is necessary to see a patient in clinic, an unscheduled visit will be scheduled appropriately.

All patients will go on a 6-week transitional diet consisting of 4 weeks of full liquid protein shakes and 2 weeks of soft pureed diet. The transitional diet is designed to allow suture healing and incorporation within the plicated gastric wall. After the transitional diet period, all patients will be on a low-calorie healthy diet personalized by the dietician according to individual patients' needs conducive to weight loss. Physical activity, including 150 minutes of aerobic exercise per week, will be encouraged and assessed for compliance during the study. It may be recommended for patients to take two chewable multivitamins and one calcium plus vitamin D supplement daily starting within 1 week of the ESG or combined HAPC and ESG.

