All patients will undergo a standard moderate intensity life-style intervention administered over 12 visits in the first year after procedure. Participants will be required to follow up with their prescribing physician to make any necessary changes to their hypertension and/or type II diabetes medications at 3, 6, 9 and 12 months. Completion of patient follow-up with providers for medication adjustment will be captured with completion of the appropriate CRF at the corresponding visits. In the event that participants are unable to contact their physician or participants are experiencing symptoms related to the medication dosing requiring urgent action, the study team will make any necessary changes in their medication dosing and document these changes appropriately in the relevant CRFs. Any medication changes will be monitored and recorded by the study team. Laboratory testing will be obtained as detailed in the study schedule of events

Participants will return for follow-up visits per the schedule of events below. For all visits with the exception of weeks 1 and 4, an in-window visit will be considered as reporting for follow-up visits within a two-week window of the visit date.

At the time of the 6-month visit, each subject's 6-month de-identified EGD video will be shared with an external center for an additional blinded assessment of the primary endpoint (suture durability) by a qualified endoscopist. Each video will be classified objectively according to the aspect of the gastric tissue and the sutures (intact, partially intact, or open). This sharing will take place through Mayo SimpleShare system.

Schedule of Events (SOE)

Study Activity	Screening & Enroll.	Rand.	Procedure	Post-Op Call	Week 1	Week 4	Week 8	Week 12	Weeks 16, 20	Week 26 (Month 6)	Weeks 30, 36, 42, 48	Week 52 (Year 1)	Unscheduled Visit
Visit Number	-2	-1	0	1	2	3	4	5	6,7	8	9,10,11,12	13	
In-Window Day Range	45 to Rand.	60 to Proc.	00		+/- 2	+/- 3				+/- 14			
Informed Consent Form (ICF)	X												
Complete Physical Exam (CPE)*	X											X	X
Focused Physical Exam *					X								
EKG	X												
Formal nutritional assessment	X												
Formal psychology evaluation	X												
Pregnancy test **	X												
Laboratory tests ⁺	X										X		X
H-Pylori breath test (baseline only)													
Questionnaires ++	X							X		X		X	
Inclusion/Exclusion	X												
Procedure Assessment Form			X										
GERD Questionnaire & Activity Assessment Form	X				X	X	X	X	X	X	X	X	X

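### The protocol leaves research teams unblinded with no role exempted, and does not say whether the dietician or the staff who measure weight and blood pressure are masked

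*Combined protocol and SAP*

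**What the plan says.** The trial is described as single-blinded under General Description. The Randomization section sets three levels of knowledge:

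- **Participants:** "Participants will be blinded to the results of randomization", until the end of the study or a safety concern.
- **Clinical team:** the arm "will not be recorded within the EMR to reduce clinical team exposure to their randomized status for follow-up care".
- **Research team:** "Research teams will not be blinded to the randomization results". The arm is also visible in study systems: "Randomization assignment will be recorded in the EDC and subject tracking".

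Trial Intervention describes the background care. "All patients will undergo a standard moderate intensity life-style intervention administered over 12 visits in the first year after procedure". After the transitional diet, "all patients will be on a low-calorie healthy diet personalized by the dietician", and aerobic exercise is encouraged and checked for compliance. Changes to blood pressure and diabetes drugs go through the participant's own prescriber at 3, 6, 9 and 12 months. If the prescriber cannot be reached, or symptoms are urgent, "the study team will make any necessary changes in their medication dosing" and record them.

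The Schedule of Events marks the counselling row, the weight and waist form and the vital-signs form at every follow-up visit from week 1 to week 52. No section names the person who counsels or measures, or gives that person's masking status.

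**The concern.** The endoscopist cannot be masked, but people who counsel and measure afterwards can be. The protocol accepts that knowledge of the arm can matter during follow-up care, since it keeps the arm from the clinical team for that reason. It gives no matching protection to study staff at the follow-up visits.

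Lifestyle counselling is itself a weight-loss treatment. If a counsellor who knows the arm encourages one group more, or tailors the diet differently, the difference is counted as an effect of HAPC on %TBWL and %EWL. Blood pressure and waist readings leave some room for the measurer's expectation. Blinding the participant prevents neither.

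%TBWL carries weight in this trial. It is listed as secondary under Endpoints, but Power and Sample Size calls it another primary endpoint at 6 and 12 months. Analysis cannot remove a bias of this kind afterwards.

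**Working it through.** **Step 1. The visit count.** Trial Intervention gives 12 lifestyle visits. The Schedule of Events has follow-up at weeks 1, 4, 8, 12, 16, 20, 26, 30, 36, 42, 48 and 52, which is 12, so the figure is reproduced. Counselling, weight and waist, and vital signs are marked at all 12. Over the trial that is 12 × 24 = 288 visits at which counselling and measurement coincide. The post-operative call is left out because it covers only adverse events and medications. The 288 measures exposure, not bias.

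**Step 2. Who may know the arm at those visits.**

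| Role | What the protocol says | Masked? |
|---|---|---|
| Participant | Blinded | Yes |
| Clinical team | Arm kept out of EMR | Partly shielded |
| Research team | Not blinded, no exemption | No |
| Dietician or counsellor | Not placed in either team | Not stated |
| Staff who measure weight, waist, blood pressure | Not named | Not stated |
| External endoscopist, 6-month video | De-identified, blinded | Yes |

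Two features make access to the arm more likely. Randomization and Data Collection puts both the randomization schedules and the data forms in REDCap, and no role-based restriction is described. Source Documentation names REDCap for electronic source data.

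**Step 3. Which outcomes are exposed.**

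- %TBWL and %EWL: mainly through counselling. A scale reading is objective, but remote visits are allowed (Informed Consent section) with no rule for obtaining weight at them.
- Blood pressure: through the reading and, less often, through drug changes.
- Waist: through the reading. It is collected but is not a listed endpoint.
- HbA1c and other laboratory values: little room for influence on the reading.
- Questionnaires: answered by blinded participants, so little room.
- Suture durability: an external blinded read is planned.

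**Step 4. What a bias would do, if present.** The documents give no SD, alpha or effect size. Assume SDs of %TBWL of 5 and 8 points, 12 per arm, a two-sided 5% t test with 12 + 12 − 2 = 22 degrees of freedom, and no true effect. The standard error is SD × √(2/12): 2.04 points for SD 5 and 3.27 for SD 8. A bias b gives a noncentrality of b divided by the standard error, and the rejection probability follows from the noncentral t distribution.

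| Assumed bias (points) | Noncentrality, SD 5 | False-positive rate, SD 5 | Noncentrality, SD 8 | False-positive rate, SD 8 |
|---|---|---|---|---|
| 1 | 0.49 | 7.6% | 0.31 | 6.0% |
| 2 | 0.98 | 15.5% | 0.61 | 9.0% |
| 3 | 1.47 | 29.0% | 0.92 | 14.2% |

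The plan's ANCOVA would change these somewhat. The table shows sensitivity and does not estimate the bias.

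**The case against.** The other side has a good case on several points.

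- A reader might infer that the unblinded team itself delivers the programme and takes the weights. The schedule makes that plausible, but no section assigns those tasks. The dietician may belong to the shielded clinical team. What the documents support is that masking is unstated.
- A reader might infer that the whole programme is individualised. The protocol calls it standard and gives everyone the same transitional diet and exercise target; only the later diet is personalised. Discretion remains in that diet and in the encouragement, because no script is described.
- A reader might infer that study staff routinely adjust blood pressure and diabetes drugs. They do so only as a fallback to the prescriber, with each change recorded. Insulin-dependent diabetes, HbA1c of 9 or more and poorly controlled hypertension are also excluded, so few participants should be affected.
- Blinding is not ignored. Participants are masked and are asked to tell the study team if they learn which procedure they had. The durability endpoint has an external blinded read.
- The PI needs access to the arm, or may need it, to judge whether events relate to the device or procedure and to apply the stopping rules. A blanket mask would not work.
- This is an openly single-blind pilot with no power calculation.

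These points narrow the concern to counselling and to clinic measurements. They do not answer it, because none of the safeguards reaches a counsellor or measurer who counts as research staff.

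**Conclusion.** The concern holds in a limited form. As written, the people who counsel participants and measure weight, waist and blood pressure may know the arm, because the only statement about study staff is that they are not blinded. Bias in %TBWL, %EWL and blood pressure is possible; nothing in the documents shows that it will occur.

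Its size cannot be derived. It is tempting to take the roughly 3% weight loss that Background gives for lifestyle modification alone and suppose that a third to a half of it differs by arm, giving 1 to 1.5 points. The documents do not support this: the 3% is not the added effect of counselling after ESG, and the fraction has no source. The Step 4 figures likewise rest on assumed SDs and assumed biases. They suggest a modest effect on false positives at 1 point and a material one at 2 to 3 points.

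The change should be made because it is cheap and the bias could not be corrected later. It does not call the durability read into question.

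**What to change.** Replace the sentence on research teams in the Randomization section with:

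> The endoscopist, procedure-room staff, the person who runs the randomization, and the PI and staff responsible for safety may know the assignment. Dieticians, lifestyle counsellors and staff who measure weight, waist and vital signs or give questionnaires are masked, except under the unblinding rule.

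Then:

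1. Use REDCap user rights to hide the assignment field and the Procedure Assessment Form from the masked roles, and remove the arm from their subject tracking view.
2. Where a small team cannot separate roles, use scripted counselling, a standard weighing procedure that also covers remote visits, and a log of contacts.
3. Report contacts and medication changes by arm.

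The cost is protocol wording and access settings, with no new staff required. The downside is in rostering: a coordinator who works on procedure day should not take follow-up measurements where this can be avoided. Item 2 covers the cases where it cannot.
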